2.2.3 Pharmacokinetic Outcome Measures

Pharmacokinetics and immunogenicity may be explored in relation to the pharmacodynamics of blood and/or CSF biomarkers in both cohorts. Serum concentration of ocrelizumab may be measured at Weeks 12, 24, 48, and 52; in the case of early termination; and at safety follow-up. The level of ocrelizumab may be measured in the CSF at Weeks 12, 24, and/or 52 for the RMS cohort; and at Week 52 for the PPMS cohort; and/or in a CSF sample taken at an unscheduled visit or from an optional sample.

Assessment may include, but may not be limited to, the relationship of pharmacokinetics in CSF to levels of cells in CSF, or to NfL levels in CSF, and/or compared with serum concentration.

2.2.4 Immunogenicity Outcome Measures

- Incidence of anti-drug antibodies (ADAs) to ocrelizumab.

2.2.5 Safety Outcome Measures

- Exposure to ocrelizumab, including information such as duration and dosage
- Incidence of
- Treatment emergent adverse events
- Serious treatment emergent adverse events

- Treatment emergent adverse events of special interest
- Treatment emergent adverse events leading to withdrawal of treatment
- Fatal adverse events
- Infusion-related reactions (IRR)
- Listing of lab abnormalities as needed

2.3 DETERMINATION OF SAMPLE SIZE

The sample size calculations for this study are based on the assumed reduction from baseline in NfL at Weeks 24 and 52 combined (Arms 2 and 3) in the RMS cohort. Other biomarker measures are not considered for power determination.

Assuming (a) a 30% reduction from pre-treatment NfL (mean [SD] = 860 pg/mL [780 pg/mL]) to posttreatment NfL (mean [SD] = 602 pg/mL [310 pg/mL]) and a correlation coefficient of 0.6, resulting in an SD of 643 pg/mL for the change from pre- to post-treatment, and (b) a desired power of 80% with a Type 1 error of 5%, a sample size of 51 patients is required, with approximately 25 patients in Arm 2 and 26 patients in Arm 3.

This is the first study to explore the impact of ocrelizumab on CSF B-cell count. In a study by Piccio et al. (2010), the rate of undetectable B cells in CSF was 74% (21/26) after 24–30 weeks of rituximab as an add-on to immunomodulatory therapy. Based on this information and a sample size of 51 patients (Arm 2 and 3 combined), the expected 95% CI for the CSF Bcell undetectable rate will be: (0.61, 0.85).

In the RMS cohort, 15 patients will be included in Arm 1 to explore the possible reduction in NfL at Week 12 post-treatment and 15 patients will be assigned to the delayed start RMS control arm (Arm 4). At least 15 patients will be recruited to the PPMS cohort. The above sample sizes are not based on statistical considerations and are meant to help explore the changes in biomarkers and generate hypotheses for future studies.

Based on the above, the total sample size for this study will be at least 96 patients. The sample size will be increased by approximately 10% in order to account for potential missing post-treatment CSF information; therefore, the number of patients to be enrolled in the RMS cohort will be $N = 88$ (Arm 1: 16 patients, Arm 2: 28 patients, Arm 3: 28 patients, and Arm 4: 16 patients).

The PPMS cohort will enroll at least 16 patients, and additional PPMS patients were allowed to enroll to collect more information on biomarkers. The total sample size of the PPMS cohort may approximate 30 patients. Therefore, the total number of patients to be enrolled is at least 104, and may reach approximately 130 patients.

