6.1 DETERMINATION OF SAMPLE SIZE

The sample size calculations for this study are based on the assumed reduction from baseline in NfL ([Gunnarsson et al. 2011](#)) at Weeks 24 and 52 combined (Arms 2 and 3) in the RMS cohort. Other biomarker measures are not considered for power determination.

Assuming (a) a 30% reduction from *pre-treatment* NfL (mean [SD]=860 pg/mL [780 pg/mL]) to *post-treatment* NfL (mean [SD]=602 pg/mL [310 pg/mL]) and a correlation coefficient of 0.6, resulting in an SD of 643 pg/mL for the change from *pre-* to *post-treatment*, and (b) a *desired* power of 80% with a Type 1 error of 5%, a sample size of 51 patients is required, with approximately 25 patients in Arm 2 and 26 patients in Arm 3.

This is the first study to explore the impact of ocrelizumab on CSF B-cell count. In a study by Piccio et al. ([2010](#)), the rate of undetectable B cells in CSF was 74% (21/26) after 24–30 weeks of rituximab as an add-on to immunomodulatory therapy. Based on this information and a sample size of 51 patients (Arm 2 and 3 combined), the expected 95% CI for the CSF B-cell undetectable rate will be: (0.61, 0.85).

In the RMS cohort, 15 patients will be included in Arm 1 to explore the possible reduction in NfL at Week 12 post-treatment and 15 patients will be assigned to the delayed start RMS control arm (Arm 4). Fifteen patients will be recruited to the PPMS cohort. The above sample sizes are not based on statistical considerations and are meant to help explore the changes in biomarkers and generate hypotheses for future studies.

Based on the above, the total sample size for this study will be 96 patients. The sample size will be increased by approximately 10% in order to account for potential missing post-treatment CSF information; therefore, the number of patients to be enrolled in the RMS cohort will be N=88 (Arm 1: 16 patients, Arm 2: 28 patients, Arm 3: 28 patients, and Arm 4: 16 patients), and N=16 in the PPMS cohort. Therefore, the total number of patients to be enrolled is 104.

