4. STATISTICAL METHODS

This study is designed to assess levels of NfL, levels of lymphocyte populations in CSF, and to generate hypotheses about biomarkers of ocrelizumab treatment in patients with RMS and PPMS. Levels of NfL in CSF and levels of lymphocyte populations in CSF will be compared to baseline levels. In addition, Arm 1 of the RMS cohort (first LP at first dose and second LP at 12 weeks) will be compared to Arm 4 (first LP at 12 weeks before and second LP at the first dose of study drug).

In this exploratory biomarker study, the analyses will be mostly descriptive and hypothesis-generating. Unless otherwise specified, statistical tests will be two-sided and the statistical significance level will be 5%. Corresponding 95% confidence intervals will be presented as appropriate. No corrections for multiple testing will be applied to the primary endpoint analyses, exploratory endpoint analyses, or interim analyses.

The statistical summaries will be descriptive if not otherwise specified. For continuous variables, the mean, median, standard deviation, 25th and 75th percentiles, minimum and maximum will be calculated. For categorical variables, number and percentage in each category will be displayed.

When establishing statistical significance, the non-parametric method will be applied as appropriate, i.e., the Mann-Whitney test will be used between two groups and the Kruskal-Wallis test will be used for three or more groups. For the analysis of continuous data, the paired/unpaired t-test and non-parametric test (i.e., the Wilcoxon matched pairs test) will be performed as appropriate. Some variables may be appropriately transformed as needed (e.g., log transformation of CSF NfL level, CD19+ B cell and CD3+ T cell numbers) before performing statistical analysis. The Spearman's rank-correlation coefficient will be used to evaluate the relationship among the levels of biomarkers or between levels of biomarkers and clinical parameters.

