4.4 EFFICACY ANALYSIS

All biomarker assessments (scheduled or unscheduled) will be summarized after applying visit windows. Summary of the visit windowing rules can be found in Appendix 2. See Module 3 for full visit window specifications. If multiple values of the same parameter occur within the same time window for blood biomarkers

Ocrelizumab—Genentech, Inc.

15/Statistical Analysis Plan ML29966

or regular lab values, the worst value for that parameter will be presented in the summary table. If multiple MRI scans occur within the same time window, the scan closest to the scheduled visit date will be included in the analysis.

All summaries will be done based on the ITT population and summaries will be provided by the actual arm, as determined by the actual timing of 2nd LP:

For patients randomized to Arm 1-3,

If the second LP date is missing then patient is included in the arm where originally randomized to;

Else:

Study Day of second LP (= date of the 2nd LP – 1st infusion start date +1)	Treatment Arm
≤126	Arm 1
127-266	Arm 2
≥267	Arm 3

Patients randomized to Arm 4 will be summarized as Arm 4 regardless of the timing of 2nd LP.

Unless otherwise specified and where appropriate, statistical tests, if any, will be performed at the two-sided 5% significance level. Corresponding 95% confidence intervals will be presented as appropriate. No corrections for multiple testing will be applied.

For biomarkers measured below the lower limit of quantification (LLOQ), numeric values will be imputed using half of the LLOQ.

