4.4.1 Primary Endpoints

For RMS cohort arm 1-3, the following values at treatment baseline and post-baseline visits, and changes and percent changes from treatment baseline to post-baseline visits will be summarized by arm:

- Levels of NfL in CSF
- Number of CD19 + B cells in CSF
- Number of CD3+T cells in CSF

The median (IQR) value at pre-treatment baseline, treatment baseline and post-baseline visits will be plotted over time and color coded by each arm. Scatter points of data will be laid over the median (IQR) plot.

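### The plan states a confidence interval for the proportion of patients with undetectable CSF B cells, but no endpoint or analysis section defines or estimates that proportion

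*SAP*

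**What the plan says.** **Planning.** SAP 2.3 cites an earlier rituximab add-on study in which "the rate of undetectable B cells in CSF was 74% (21/26) after 24–30 weeks of rituximab". From this, and from "a sample size of 51 patients (Arm 2 and 3 combined"), it concludes that "the expected 95% CI for the CSF Bcell undetectable rate will be: (0.61, 0.85"). Protocol 6.1 has the same sentence: "the expected 95% CI for the CSF B-cell undetectable rate will be: (0.61, 0.85"). The 51 patients come from the NfL calculation ("a desired power of 80% with a Type 1 error of 5%, a sample size of 51 patients is required"); the same section says no other biomarker was used for power.

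**Endpoint.** SAP 2.2.1 makes change in CSF CD19+ B-cell number, in cells per microliter, one of three primary endpoints for RMS Arms 1–3.

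**Analysis.** SAP 4.4.1 summarises values at treatment baseline and at later visits, and "changes and percent changes from treatment baseline to post-baseline visits will be summarized by arm". It adds a median (IQR) plot with individual points overlaid. SAP 4.4.2.1 pools arms for blood biomarkers and does not mention pooling for CSF. For any biomarker below the LLOQ, SAP 4.4 says "numeric values will be imputed using half of the LLOQ".

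**Not found.** The undetectable rate does not appear in SAP 2.2.1, 2.2.2, 4.4.1, 4.4.2, 4.4.3 or 4.4.4, nor in Protocol 6.4.1 or 6.4.2. Neither document gives an LLOQ for the CSF cell count or says whether a count of zero falls under the half-LLOQ rule.

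**The concern.** The only precision stated for CSF B cells belongs to a quantity that the plan then drops. The sample-size section treats the result as a proportion cleared, in two arms pooled. The analysis section treats it as change in a count, arm by arm.

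The plan itself expects about three quarters of post-treatment samples to be undetectable. Most post-treatment values would then be one repeated number, and a median or percent change says little about how many patients were cleared. Percent change carries a further risk: if undetectable is recorded as half the LLOQ, two patients with equally complete clearance get different results because they started at different levels. A patient below the LLOQ at both LPs shows 0%, the same as a patient with a detectable count that did not move.

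At stake is how clearly the study reports its most direct CNS readout of the drug's mechanism. Whether it can show a fall is not in doubt.

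**Working it through.** **Inputs.** Assumed undetectable rate 74%, printed with the fraction 21/26; n = 51 for Arms 2 and 3 combined; planned enrolment of 28 in each of these arms, with 25 and 26 evaluable (all SAP 2.3). Floor rule of half the LLOQ (SAP 4.4).

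**1. Reproduce the stated interval.** 0.74 × 51 = 37.7, so take 38/51 = 0.745. The 95% limits are:
- Agresti-Coull (0.610, 0.846) and Jeffreys (0.614, 0.849), both of which round to the printed (0.61, 0.85);
- Wilson (0.611, 0.845);
- Clopper-Pearson (0.604, 0.857).

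The interval follows from 74% and n = 51.

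**2. Check the printed rate.** 21/26 = 0.808, not 0.74. At 80.8%, 0.808 × 51 = 41.2. Taking 41/51 = 0.804, the Wilson interval is (0.675, 0.890), about (0.68, 0.89). The percentage and the fraction cannot both be right, and the interval depends on which is used.

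**3. Effect of dropping the pooling.** For one arm of about 26 at 74%, the Wilson interval is (0.55, 0.87), a width of 0.32. The stated pooled interval has width 0.85 − 0.61 = 0.24.

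**4. Where the post-treatment median falls.** Let X be the number at the floor in an arm, X ~ Binomial(n, p). With n = 28 the median averages the 14th and 15th ordered values, so it equals the floor only if X ≥ 15.

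| n | needed at floor | p = 0.74 | p = 21/26 |
|---|---|---|---|
| 28 | 15 | 0.994 | above 0.999 |
| 26 | 14 | 0.993 | above 0.999 |
| 51 | 26 | above 0.999 | above 0.999 |

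For the whole IQR to collapse to the floor at n = 28, at least 22 must be there: P(X ≥ 22) = 0.38 at p = 0.74 and 0.72 at 21/26.

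**5. Percent change in a cleared patient.** Suppose undetectable is recorded as half the LLOQ and baseline is m × LLOQ. Then percent change = (0.5/m − 1) × 100.

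| baseline (× LLOQ) | percent change |
|---|---|
| 1.2 | −58% |
| 2 | −75% |
| 5 | −90% |
| 10 | −95% |
| below LLOQ at both LPs | 0% |

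If undetectable is recorded as zero instead, every cleared patient with a detectable baseline shows −100%, and percent change from a zero baseline is undefined. The SAP does not say which case applies.

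**6. Does the planned analysis still show a fall?** Yes. In a simulation with assumed lognormal baselines, 0 to 50% of them undetectable, post-treatment undetectable rates of 0.74 or 0.81 and n = 51, the Wilcoxon test on change was significant in essentially every run.

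**The case against.** A reader might infer that the plan does not measure depletion at all. The documents do not support that. CSF CD19+ count is a primary endpoint, and SAP 4.4.1 reports post-treatment values as well as change and percent change, with individual points plotted. SAP 4 adds quartiles, minimum and maximum, and allows log transformation and matched-pairs testing. SAP 4.4.3 allows a model adjusted for baseline level. Step 6 confirms that a fall would be seen.

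A reader might also infer that patients at the floor at baseline are counted as treatment failures. No responder rule exists for any CSF biomarker; such patients contribute a zero change and nothing more. Nor is it established that the IQR will collapse: at 74% that is less likely than not (0.38).

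Four further objections have weight:
- The percent-change figures in step 5 assume that undetectable counts fall under the half-LLOQ rule. That is one of two possible readings.
- The interval illustrates precision using another drug's data. It did not set the sample size, and the Version 5 synopsis in SAP Appendix 1 omits that sentence.
- The study is mostly descriptive and hypothesis-generating. This lowers the stakes, but the missing item is itself descriptive.
- SAP 4.9 places the list of outputs in Module 2, which was not available. It may contain a table of the rate. The definition would still belong in the SAP text.

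None of these supplies a definition of undetectable or an analysis of the rate.

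**Conclusion.** The point holds as a gap between planning and analysis. Both current sample-size sections state an expected interval of (0.61, 0.85) for a rate that no available endpoint or analysis section defines or estimates, and the pooling behind that interval is not carried into the CSF analysis. The plan will detect a fall in CSF CD19+ count. What it lacks is the proportion of patients cleared, with its interval.

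At the plan's 74%, the post-treatment median in an arm of 28 is almost certainly the floor value (probability 0.994). This assumes that the rituximab rate carries over to ocrelizumab and that all undetectable samples share one recorded value. The dependence of percent change on baseline is conditional on the half-LLOQ rule applying to these counts. Where it does apply, it also reaches the Arm 1 versus Arm 4 comparison, because SAP 4.4.2.2 moves to percent change when data are highly skewed.

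Separately, 74% and 21/26 disagree and must be reconciled. The change is worth making, but the primary analysis does not fail without it.

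**What to change.** 1. In SAP 4.4, define undetectable for CSF CD19+ B cells: give the detection limit or LLOQ, and say whether a zero count is kept as zero or set to half the LLOQ.
2. In SAP 4.4.1, beside the existing change summaries, report n/N undetectable with a 95% CI (method named) at treatment baseline and at the post-treatment LP. Show it by arm and for Arms 2 and 3 combined, for all patients and for those detectable at treatment baseline.
3. In SAP 2.3 and Protocol 6.1, correct either the 74% or the 21/26. If 80.8% is right, restate the expected interval, about (0.68, 0.89) by Wilson at 41/51.
4. Check SAP Module 2. If the table is already listed there, only the definition, a cross-reference and item 3 remain.

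The cost is a few lines of SAP text, a matching correction in the protocol and one table from data already collected. The analysis is descriptive, so it needs no multiplicity adjustment. The small downside is a wider interval in the detectable-at-baseline subset, because fewer patients enter it.

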2.4 ANALYSIS TIMING

For publication purpose, an interim analysis (Interim Analysis 1, details specified in SAP version 1) has been conducted based on a clinical data cutoff date (CCOD) of June 1st, 2017. Biomarker data collected from RRMS Arm 1 and Arm 2 patients were summarized based on available data. Blood NfL analyte data was not available at the time of Interim Analysis 1, a post-hoc analysis may be conducted for blood NfL data with CCOD of June 1st 2017 upon its availability.

Table 1 shows the timing of planned interim and final analyses for the main study and LTE period. Additional interim analyses may also be performed for internal exploration and/or publication purposes. No formal adjusting of alpha level is necessary for the multiple interim analyses, as no decisions will be made regarding study conduct based on the interim analyses results.

Table 1 Outline of Analysis Timings

Analysis	Timing of Analysis
Interim Analysis 1	Approximately 50% of patients have had their second LP (CCOD June 1 st 2017) Refer to SAP for IA1 for analysis details
Interim Analysis 2	Addition IA planned for publication needs. E.g., when RMS Arm1-4 patients complete 2 nd LP.
Interim Analysis 3 (Internal review)	Approximately 50% of PPMS patients had their 2 nd LP
Final Analysis	RMS and PPMS patients complete Main Treatment Period
LTE Final Analysis	All patients complete the LTE period (4-Year summary) & Safety Follow-up assessments

3. STUDY CONDUCT

3.1 RANDOMIZATION ISSUES

Patients in Arms 1-3 of the RMS cohort will be randomized into each of the three arms at 1:1:1 ratio where the timing of the second LP will be at Week 12, 24, or 52, respectively, following the first dose of Ocrelizumab. An independent interactive voice/web response system (IXRS) provider will conduct randomization and maintain the treatment assignment code. Randomization will be stratified by the previous disease-modifying therapy (DMT) treatment status (DMT-naïve vs. DMT-experienced). Therefore, the proportion of DMT-naïve patients will be approximately equal in each of three arms.

In the event that one of the randomized arms (e.g., Arm 1) reached the planned target patient enrollment (e.g., ~16 patients in Arm 1), subsequent new patients will be randomized into the remaining arms (e.g., Arm 2 and 3) at a 1:1 ratio.

Arm 4 of the RMS cohort with delayed treatment will not be part of the randomization and will be recruited separately.

4. STATISTICAL METHODS

This study is designed to assess levels of NfL, levels of lymphocyte populations in CSF, and to generate hypotheses about biomarkers of ocrelizumab treatment in patients with RMS and PPMS. Levels of NfL in CSF and levels of lymphocyte populations in CSF will be compared to baseline levels. In addition, Arm 1 of the RMS cohort (first LP at first dose and second LP at 12 weeks) will be compared to Arm 4 (first LP at 12 weeks before and second LP at the first dose of study drug).

In this exploratory biomarker study, the analyses will be mostly descriptive and hypothesis-generating. Unless otherwise specified, statistical tests will be two-sided and the statistical significance level will be 5%. Corresponding 95% confidence intervals will be presented as appropriate. No corrections for multiple testing will be applied to the primary endpoint analyses, exploratory endpoint analyses, or interim analyses.

The statistical summaries will be descriptive if not otherwise specified. For continuous variables, the mean, median, standard deviation, 25th and 75th percentiles, minimum and maximum will be calculated. For categorical variables, number and percentage in each category will be displayed.

When establishing statistical significance, the non-parametric method will be applied as appropriate, i.e., the Mann-Whitney test will be used between two groups and the Kruskal-Wallis test will be used for three or more groups. For the analysis of continuous data, the paired/unpaired t-test and non-parametric test (i.e., the Wilcoxon matched pairs test) will be performed as appropriate. Some variables may be appropriately transformed as needed (e.g., log transformation of CSF NfL level, CD19+ B cell and CD3+ T cell numbers) before performing statistical analysis. The Spearman's rank-correlation coefficient will be used to evaluate the relationship among the levels of biomarkers or between levels of biomarkers and clinical parameters.

4.1 ANALYSIS POPULATIONS

One patient population will be defined for the purpose of the safety analysis, and two patient populations will be defined for the efficacy analysis. All primary efficacy analyses will be performed using the intent-to-treat (ITT) population. The biomarker population was used in the *Interim Analysis 1* on summaries of all biomarker parameters. It may not be used in the other planned analyses if, based on the timing of planned analyses, the biomarker population will be approximately the same as the ITT population. Demographics, baseline MRI, and disease history will be summarized using the enrolled population, defined as all

patients who were enrolled in the study, regardless of whether they received any Ocrelizumab.

4.1.1 Intent-to-treat (ITT) Population

The ITT population is defined as all patients enrolled in the study who received at least one dose of Ocrevus. Summaries such as patient disposition and baseline biomarkers will be performed on the ITT population. Summaries of all primary and exploratory endpoints will also be performed using the ITT population.

Patients in this study were randomized/assigned into arms to take the 2nd LP at different timings, while receiving the same treatment. In order to summarize the effect of ocrelizumab on biomarkers over time more accurately, patients will be summarized by the actual “arm” depending on when the patient actually received the 2nd LP.

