6.4 ANALYSES

Statistical analyses will be performed on the analysis population, defined as all enrolled patients who (a) received at least one infusion of ocrelizumab, even if the infusion was incomplete or (b) received at least one LP.

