4.4.2 Exploratory Endpoints

4.4.2.1 Summaries of Exploratory Endpoints Over Time

For RMS patients in Arm 4, values at pre-treatment baseline and treatment baseline, and change and percent change from treatment baseline to post-baseline visits will be summarized.

For RMS patients in arms 1-3 and PPMS patient arm, CSF biomarker endpoints, blood biomarker endpoints and MRI biomarker endpoints stated in Section 2.2.2 will be summarized over time following the same rule as the primary efficacy endpoint, as stated in Section 4.4.1. The median (IQR) value of CSF and blood biomarkers at pre-treatment baseline, treatment baseline and post-baseline visits will be plotted over time and color coded by each arm. Scatter points of data will be laid over the median (IQR) plot for blood NfL level, CD19+ B cell and CD3+ T cell numbers.

Mean (SD) of MRI biomarker endpoints will be summarized over time.

For blood biomarkers, patient arms will also be pooled to look at the effect of ocrelizumab over time.

4.4.2.2 Comparison between Arm 1 and Arm 4

For patients in Arm 4, changes from pre-treatment baseline to treatment baseline will be compared to Arm 1 change from treatment baseline to Week 12 through an ANCOVA model adjusting for baseline DMT status (DMT naïve vs. DMT experienced) and baseline biomarker level for the following endpoints:

- CSF CD19+ B cell, CD3+ T cell and NfL
- Blood CD19+ B cell, CD3+ T cell and NfL

If data are highly skewed, ANCOVA model will be based on percent changes.

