4.9 SCOPE OF PLANNED ANALYSES

Interim Analysis 1 was limited to patients in the RMS cohorts Arms 1-3 who were enrolled by the CCOD. Biomarker analyses were limited to the Biomarker Population.

Interim Analysis 2 will be limited to patients in the RMS cohort Arms 1-4. Only data during the Main Treatment Period (defined in Section 2, before receiving Week 72 treatment) will be summarized at this interim analysis, which applies to patient disposition information, efficacy endpoints and safety endpoints.

The Final Analysis will include all patients (RMS cohort Arms 1-4 and PPMS cohort). Only data during the Main Treatment Period will be summarized.

The LTE Final Study Analysis will include all patients and all data collected during the Long Term Extension Period and the Safety Follow Up period.

The endpoints that will be included in each of the analyses and the analysis populations are specified in Table 2. Specific list of planned outputs will be available in SAP Module 2.

Table 2 Scope of Planned Analyses

Endpoint	Interim Analysis 1	Interim Analysis 2	Final Analysis	LTE Final Analysis
Disposition & Baseline Demographics, characteristics	X (RMS Enrolled Population, Biomarker Population)	X (RMS Enrolled Population)	X (Enrolled Population)	X (Enrolled Population)
Efficacy Endpoints (depend on data availability)	X (RMS Biomarker Population)	X Selected biomarkers as specified in SAP Module 2. (RMS Enrolled Population)	X (Enrolled Population, Per-Protocol Population)	X (Enrolled Population, Per-Protocol Population)
Pharmacokinetic (depend on data availability)	Not Planned	Depend on data availability	X (Pharmacokinetic Evaluable Population)	X (Pharmacokinetic Evaluable Population)
Exposure, AE, IRR	X (RMS Safety Population)	X (RMS Safety Population)	X (Safety Population)	X (Safety Population)
ADA	Not Planned	Not Planned	X (Safety Population)	X (Safety Population)
Vital Signs and General Laboratory Data	Not Planned	Not Planned	X (Safety Population)	X (Safety Population)

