Investigational Medicinal Products

Test Product (Investigational Drug)

The investigational medicinal product for this study is ocrelizumab.

Non-Investigational Medicinal Products

Premedicate with 100 mg of methylprednisolone (or an equivalent) approximately 30 minutes prior to each ocrelizumab infusion *and with an antihistaminic drug (e.g., diphenhydramine) approximately 30 – 60 minutes before each infusion of ocrelizumab* to reduce the frequency and severity of infusion-related reactions (IRRs).

The addition of an antipyretic (e.g., acetaminophen/paracetamol) may also be considered *to further reduce the frequency and severity of IRRs*.

Statistical Methods

Statistical analyses will be performed on the analysis population, defined as all enrolled patients who received at least one infusion of ocrelizumab, even if the infusion was incomplete.

Primary Endpoints

Primary endpoints for the RMS cohort include:

- Change in levels of NfL in CSF from treatment baseline to post-treatment with ocrelizumab
- Change in number of CD19+ B cells in CSF from treatment baseline to post-treatment with ocrelizumab
- Change in number of CD3+ T cells in CSF from treatment baseline to post-treatment with ocrelizumab

Determination of Sample Size

The sample size calculations for this study are based on the assumed reduction from baseline in NfL (Gunnarsson et al. 2011) at Weeks 24 and 52 combined (Arms 2 and 3) in the RMS cohort. Other biomarker measures are not considered for power determination.

Assuming (a) a 30% reduction from pre-treatment NfL (mean [SD] = 860 pg/mL [780 pg/mL]) to post-treatment NfL (mean [SD] = 602 pg/mL [310 pg/mL]) and a correlation coefficient of 0.6, resulting in an SD of 643 pg/mL for the change from pre- to post-treatment, and (b) a desired

power of 80% with a Type 1 error of 5%, a sample size of 51 patients is required, with approximately 25 patients in Arm 2 and 26 patients in Arm 3.

This is the first study to explore the impact of ocrelizumab on CSF B-cell count. In a study by Piccio et al. (2010), the rate of undetectable B cells in CSF was 74% (21/26) after 24–30 weeks of rituximab as an add-on to immunomodulatory therapy.

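### With narrow exceptions, SAP adverse event summaries omit LP-related events that start before first dose, although sample-collection events are a safety objective; separately, SAP 4.1.1/4.4 and Table 2 name different efficacy populations

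*SAP*

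**What the plan says.** **Adverse events.** Protocol Version 4, section 2.5, and the Version 5 synopsis in SAP Appendix 1 both name adverse events related to sample collection as a safety endpoint. Protocol 5.2.1 gives LP before treatment assignment as an example of a source of adverse events. SAP 2.2.5 lists the safety outcomes and has none for sample collection. SAP 4.1.4 restricts the safety population to patients with an infusion, and SAP 4.6 restricts adverse event summaries to treatment-emergent events. Protocol 6.5 promises a listing of all serious adverse events and deaths; the SAP text contains no such listing.

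**Efficacy populations.** SAP 4.1 announces that "two patient populations will be defined for the efficacy analysis". SAP 4.1.1 states "The ITT population is defined as all patients enrolled in the study who received at least one dose of Ocrevus" and assigns all primary and exploratory endpoints to that set. SAP 4.4 agrees: "All summaries will be done based on the ITT population and summaries will be provided by the actual arm". SAP 4.9 then says that Table 2 specifies the populations. Its efficacy row gives the RMS Enrolled Population for Interim Analysis 2 and "Enrolled Population, Per-Protocol Population" for the Final and LTE Final Analyses. Enrolled means "patients who were enrolled in the study, regardless of whether they received any Ocrelizumab". Disposition is on ITT in SAP 4.1.1 and 4.2 and on Enrolled in Table 2. Protocol 6.4 takes patients who "received at least one infusion of ocrelizumab, even if the infusion was incomplete or (b) received at least one LP", while the Version 5 synopsis, like the Version 4 one, uses a set "defined as all enrolled patients who received at least one infusion of ocrelizumab, even if the infusion was incomplete".

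**The concern.** The study requires two LPs of each patient and undertakes to report the harm from taking samples. If the SAP is followed literally, an LP complication that begins before first dose generally does not reach an adverse event table, and one in a patient who is never dosed cannot. The clearest case is the Arm 4 LP at Week -12, about 84 days before a treatment-emergent event can begin.

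The population conflict matters mainly for Arm 4, the study's control for regression to the mean. In SAP 4.4.2.2, Arm 4 "changes from pre-treatment baseline to treatment baseline will be compared to Arm 1 change from treatment baseline to Week 12", so the control interval is complete before any drug is given. The second LP may precede dosing by up to 7 business days (Protocol Appendix 2, note p), so a patient can have both LPs and no dose. Two programmers working from the same SAP text could treat that patient differently.

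**Working it through.** **1. Pre-dose LPs.** Enrolment (SAP 2.3) is 16 + 28 + 28 + 16 RMS plus 16 PPMS = 104.
- Scheduled LPs: 104 × 2 = 208.
- Before first dose: 104 first LPs + 16 second LPs in Arm 4 = 120, and 120/208 = 58%.
- With 32 PPMS patients: (120 + 16)/(120 × 2) = 136/240 = 57%.
- Arm 4 Week -12 LPs alone: 16/208 = 8%.

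Optional LPs are not counted. A treatment-baseline LP may fall on the dosing day or a few days before it, so some of its complications will start on or after first dose and be tabulated, though not identified as LP-related.

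**2. Which LP-related events reach a SAP summary (SAP 4.1.4 and 4.6).**

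| Event | In a SAP summary? |
|---|---|
| Onset on or after first dose date | Yes, as treatment-emergent |
| Onset before first dose, worsens, ends on or after it | Yes |
| Start date completely missing | Yes, unless a complete end date precedes first dose |
| Any other onset before first dose | No |
| Any event in an undosed patient | No |

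**3. What is recorded.** The first paragraph of Protocol 5.3.1 sends all adverse events to the eCRF, and the schedules mark adverse events at screening and, for Arm 4, at Week -12. The second paragraph of 5.3.1, and 5.4.2.1, limit pre-dose reporting to serious events caused by a protocol procedure. The documents do not settle whether non-serious pre-dose events are captured.

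**4. An Arm 4 patient with both LPs and no dose.**

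| Rule | Status |
|---|---|
| SAP ITT (4.1.1, 4.4) | out |
| SAP Biomarker Population (4.1.2) | out |
| SAP Table 2, Enrolled (Interim Analysis 2, Final) | in |
| Protocol 6.4 | in |
| Version 4 and Version 5 synopses | out |

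If the patient is in, the CSF windows in SAP Appendix 2 run in study days from baseline, and the note to Protocol Table 1 counts days from first dose. No anchor is given for someone never dosed.

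In Arms 1-3 an undosed patient has no post-treatment LP, and SAP 4.7 does not impute, so change from baseline hardly depends on the choice.

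**5. Size for the Arm 1 versus Arm 4 comparison.** The plan's own figures reproduce first. The SD of change is √(780² + 310² − 2 × 0.6 × 780 × 310) = 643.7. For a difference of 860 − 602 = 258, a two-sided 5% paired t-test with 80% power needs 51 patients.

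Half-width of the 95% CI = t(0.975, 14 + n4) × SD × √(1/16 + 1/n4), with 16 patients in Arm 1 and n4 in Arm 4. Assuming SD 643 in both arms:
- n4 = 16: 464 pg/mL
- n4 = 15: 473 pg/mL
- n4 = 14: 482 pg/mL

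The first lost patient widens the interval by 472.6/464.3 = 1.018. The SD cancels in this ratio, and it stays 1.018 when two degrees of freedom are taken off for the planned ANCOVA covariates. The pg/mL widths are illustrative: the documents give no change SD for Arm 4, and SAP 4.4.2.2 moves to percent change if the data are highly skewed.

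**The case against.** **The protocol already lists the serious events.** Protocol 6.5 lists all serious adverse events and runs safety analyses on the analysis population, which under 6.4 includes a patient with an LP and no dose. If only serious procedure-caused events are collected before dosing, Version 4 already lists what exists. This stands as far as it goes. A reader might infer that the plan as a whole ignores pre-dose LP harm, and the documents do not support that. The SAP, however, drops the listing, and the non-serious events remain unresolved.

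**A table by individual LP may not be feasible.** Protocol 5.3.4 describes causality to study drug only, and no field linking a non-serious event to a given LP is described. This also stands. A listing with timing worked out from dates is what can be asked for.

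**The population conflict is minor and may be settled elsewhere.** Arm 4 is not randomised, the comparison is exploratory, and its size is not statistically based. SAP Modules 2 and 3, which hold the output list and full window rules, are not among the documents. It is therefore too strong to say that the Per-Protocol set cannot be built at all; it is undefined in the SAP text available. Correcting Table 2 alone would remove the contradiction. Keeping undosed Arm 4 patients is a further choice, justified because their control interval is complete without a dose. None of this removes the disagreement between SAP 4.4 and Table 2, or the restriction in 4.6.

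**Conclusion.** The main point holds. Under SAP 4.6, pre-dose LP-related events enter no SAP adverse event summary apart from the two exceptions above, although they belong to a stated safety objective and 58% of scheduled LPs are pre-dose. A reader might take that as the share of LP events lost. It is not, because the documents give no event rates and some events after a treatment-baseline LP will start on or after dosing.

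The population point is a consistency correction. A reader might infer a biased control comparison, but the documents do not show whether going undosed would be linked to the biomarkers, so no bias is claimed. The effect is about 1.8% in interval width for a first excluded patient (1 of 16 planned), and the number of such patients is not given and may be zero. The Arms 1-3 primary endpoints are essentially unaffected.

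The conclusion rests on the SAP text without Modules 2 and 3, and on Version 4 for the recording rules, since only the synopsis of Version 5 is available.

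**What to change.** **Adverse events (SAP 2.2.5 and 4.6).**
- Add a listing, with counts where the data allow, of recorded adverse events with onset after an LP or attributed to a protocol procedure. Cover all patients with at least one LP, including pre-dose onset and undosed patients, and show timing relative to each LP from dates.
- Restore the listing of all serious adverse events from Protocol 6.5.
- Reconcile Protocol 5.2.1, 5.3.1, 5.4.2.1 and the schedules in the current version. Because this cannot recover events that sites did not record, state in the report that non-serious pre-dose events may be incomplete.

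**Populations.**
- In Table 2, change the efficacy population to ITT for the analyses still to come, and delete or define Per-Protocol.
- In SAP 4.1.1 and 4.2, report disposition on the Enrolled Population, with the number of Arm 4 patients who had both LPs and no dose.
- In SAP 4.4.2.2, state as an explicit exception to ITT that Arm 4 patients with both pre-treatment LPs are included whether or not dosed, with windows for the undosed anchored on the second LP date.

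The cost is SAP wording, a protocol clarification, one disposition count and two listings from data already recorded. No new data collection is needed.
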